3.2. Maximum Tolerated Dose Definition

The MTD estimate is the highest dose level tested of avelumab and axitinib associated with the occurrence of DLTs within the first 2 cycles of treatment in <33% of DLT-evaluable patients.

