3.1.1.2. Dose-Finding Criteria

Dose finding will follow the mTPI method,²⁹ using doses of avelumab and axitinib as shown in Table 1.

Table 1. Dose Levels in the Dose Finding Phase

Dose Level	Avelumab	Axitinib
1 (Starting Dose Level)	10 mg/kg IV Q2W	5 mg oral BID
-1A	5 mg/kg IV Q2W	5 mg oral BID
-1B	10 mg/kg IV Q2W	3 mg oral BID

BID: twice daily; Q2W: every 2 weeks

090177e1907c3de0\0.1\Draft\Versioned On:01-Mar-2019 17:22 (GMT)

Dose de-escalation to DL-1A and DL-1B

Possible dose-finding scenarios based on the starting dose level (1) tolerability are illustrated in Table 2. DL-1A and DL-1B will be explored only if the design recommends de-escalation at DL1.

In this dosing algorithm, there are up to 3 potential dose levels (DL): (DL1) avelumab 10 mg/kg Q2W + axitinib 5 mg BID, (DL-1A) avelumab 5 mg/kg Q2W + axitinib 5 mg BID, and (DL-1B) avelumab 10 mg/kg Q2W + axitinib 3 mg BID.

Alternative doses, schedule(s), and PK time points may be reconsidered during the study based on the emerging safety and PK data.

There are several potential dose-finding sequences for avelumab in combination with axitinib. The specific sequence to be followed depends upon the number of patients enrolled in the study and the number of DLTs observed at each specific dose combination. The sequences are mutually exclusive, meaning only one of the sequences will be followed throughout the course of the study. Possible sequences are listed below in Table 2.

Table 2. Possible Dose Finding Sequences

Possible Sequences Starting with Dose Level 1
a) DL1
b) DL1 → DL-1A and DL-1B
c) DL1 → DL-1A and DL-1B → DL1

DL: dose level

Dosing will begin at DL1 and possibly be de-escalated to DL-1A and DL-1B according to [Table 1](#) and [Table 2](#).

Dose escalation from DL-1 back to DL1 will be allowed as long as DL1 has not been determined to have exceeded the MTD and the rule indicates escalation for both DL-1A and DL-1B. The escalation/de-escalation rules will follow the mTPI method.²⁹

Briefly, the mTPI method relies upon a statistical probability algorithm, calculated using all patients treated in prior and current cohorts at the same dose level to determine where future cohorts should involve dose escalation, no change in dose, or dose de-escalation. The detailed dose-finding rules based on the mTPI are illustrated in [Table 3](#).

Table 3. Detailed Dose Escalation/De Escalation Scheme

		Number of patients treated at current dose					
		1	2	3	4	5	6

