Number of Toxicities	0	E	E	E	E	E	E
	1	D	S	S	S	S	E
	2		DU	D	S	S	S
	3			DU	DU	D	D
	4				DU	DU	DU
	5					DU	DU
	6						DU

E = Escalate to the next higher dose

S = Stay at the current dose

D = De-escalate to the next lower dose

U = The current dose is unacceptably toxic

Note: for the initial dose level (ie, “DL1”) evaluated, the doses are maintained (“S”), while DL-1A or DL-1B may be escalated (“E”).

As an example, if the total number of patients treated at DL1 is 3, the following dosing rules are applied:

- 0 - 1 DLTs → remain at the same dose (DL1);
- 2 DLTs → de-escalate to DL-1 and allow for possible escalation back to DL1;
- 3 DLTs → de-escalate to DL-1 and consider DL1 as intolerable.

If the dose is de-escalated to DL-1A and DL-1B and the total number of patients then treated at DL-1A and DL-1B is 3, the following dosing rules are applied within each dose level:

- 0 DLTs (in DL-1A and DL-1B) → escalate back to DL1;
- 1 DLT (in either DL-1A or DL-1B) → remain at the same DL (DL-1);
- 2-3 DLTs (in either DL-1A or DL-1B) → de-escalation not possible and depending on the distribution of the DLTs one or both doses at DL-1 will be considered intolerable.

Rules for dose-finding, using the mTPI method, include the following:

- The target enrollment cohort size is 3 patients. However, patients may be enrolled in cohort sizes of 3-4 depending on the number of potential patients identified at participating sites. The patients treated at each dose level may initiate dosing simultaneously. If the first 2 patients experience a DLT prior to enrollment of the third one, the dose level will be deemed intolerable and the dose level will be de-escalated.

090177e1907c3de0\0.1\Draft\Versioned On:01-Mar-2019 17:22 (GMT)

- The next cohort may be enrolled when all patients at the current dose cohort have been evaluated for 4 weeks (ie, the first 2 treatment cycles), or experience a DLT, whichever comes first.
- If a patient withdraws from study treatment before receiving at least 75% of the planned first 2 cycles of axitinib or 2 infusions of avelumab for reasons other than study drug-related toxicity, another patient will be enrolled to replace that patient at the current dose level.

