- The dose-finding component of the trial is completed when 6 DLT-evaluable patients have been treated at the highest dose associated with DLT rate <0.33 . It is estimated that approximately 15 DLT-evaluable patients will need to be enrolled to reach 6 DLT-evaluable patients at the estimated MTD.
- The RP2D will be confirmed in the Dose Expansion Phase, taking into account the MTD determination from the Dose Finding Phase, and other factors related to safety, efficacy, PK, and PD involving all available data from test cohorts.

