The 3 dosing intervals are associated with 3 different dose-escalation decisions. The under-dosing interval corresponds to a dose escalation (E), over-dosing corresponds to a dose de-escalation (D), and proper-dosing corresponds to remaining at the current dose (R). Given a dosing interval and a probability distribution, the UPM of that dosing interval is defined as the probability of a patient belonging to that dosing interval divided by the length

of the dosing interval. The mTPI design calculates the UPMs for the 3 dosing intervals, and the one with the largest UPM informs the corresponding dose-finding decision, which is the dose level to be used for future patients. For example, if the under-dosing interval has the largest UPM, the decision will be to escalate, and the next cohort of patients will be treated at the next higher dose level. Ji and collaborators²⁹ have demonstrated that the decision based on UPM is optimal in that it minimizes a posterior expected loss (ie, minimizes the chance of making a wrong dosing decision).

The dose finding component of the trial (Phase 1) uses a modified version of the mTPI design that maximizes the number of evaluable patients treated at each dose level at 6. Dose finding is completed when 6 evaluable patients have been treated at the highest dose with DLT rate <0.33.

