The 3 dosing intervals are associated with 3 different dose-escalation decisions. The under-dosing interval corresponds to a dose escalation (E), over-dosing corresponds to a dose de-escalation (D), and proper-dosing corresponds to remaining at the current dose (R). Given a dosing interval and a probability distribution, the unit probability mass (UPM) of that dosing interval is defined as the probability of a patient belonging to that dosing interval divided by the length of the dosing interval. The mTPI design calculates the UPMs for the 3 dosing intervals, and the one with the largest UPM informs the corresponding dose-finding decision, which is the dose level to be used for future patients. For example, if the under-dosing interval has the largest UPM, the decision will be to escalate, and the next cohort of patients will be treated at the next higher dose level. Ji and collaborators have demonstrated that the decision based on UPM is optimal in that it minimizes a posterior expected loss (ie, minimizes the chance of making a wrong dosing decision).

The dose finding phase of the trial uses a modified version of the mTPI design that maximizes the number of evaluable patients treated at each dose level at 6. Dose finding is completed when 6 DLT-evaluable patients have been treated at the highest dose with a DLT rate  $< 0.33$ .

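### Do the dose-finding rules leave 2 DLTs in 6 evaluable patients without a usable decision, and does that need a change?

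*Protocol*

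**What the plan says.** Five statements bear on the point.

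- **MTD.** Protocol 3.2 defines it as the highest level tested "associated with the occurrence of DLTs within the first 2 cycles of treatment in <33% of DLT-evaluable patients".
- **Decision table.** Protocol 3.1.1.2, Table 3, has S in the cell for 2 toxicities among 6 patients, with the key "S = Stay at the current dose". The table has no column beyond 6.
- **Cap.** Protocol 9.2.1 uses a version of mTPI that "maximizes the number of evaluable patients treated at each dose level at 6", and SAP 5.1.2 repeats this.
- **Completion.** Under Protocol 3.1.1.2, dose finding is "completed when 6 DLT-evaluable patients have been treated at the highest dose associated with DLT rate" below 0.33. The SAP has the same rule: "Dose finding is completed when 6 DLT-evaluable patients have been treated at the highest dose with a DLT rate" below 0.33.
- **Opening the lower levels.** Protocol 3.1.1.2 says "DL-1A and DL-1B will be explored only if the design recommends de-escalation at DL1". Protocol 3.1 and SAP 2.2 instead make it conditional on the MTD having been exceeded at DL1, and do not define that condition.

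SAP Section 6 adds that, by the time of SAP V2, dose finding had been completed, with DL1 (with or without the axitinib lead-in) the only dose level used and no randomization to come.

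**The concern.** Estimating the MTD is part of the primary objective, so every reachable outcome ought to lead to one action. At 2 of 6 it seems not to. The observed rate is just over the limit, so DL1 is not the MTD. The table says to stay, but the cap prevents another evaluable patient. Under Protocol 3.1.1.2, Stay is not a recommendation to de-escalate, so DL-1A and DL-1B remain closed and the completion rule cannot be met. The next step would then be settled case by case.

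A second tension appears at 2 DLTs in the first 3 patients. The instruction there is to "de-escalate to DL-1 and allow for possible escalation back to DL1", and "Dose escalation from DL-1 back to DL1 will be allowed as long as DL1 has not been determined to have exceeded the MTD". If the lower levels may open only once the MTD has been exceeded at DL1, as Protocol 3.1 puts it, a later return to DL1 looks contradictory.

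**Working it through.** **1. Is Table 3's Stay at 2 of 6 a misprint?** The documents give neither the prior nor the cutoff for the unacceptable-toxicity flag. Assume a Beta(1,1) prior and a cutoff of 0.95 on P(p > 0.33). After 2 DLTs in 6 the posterior is Beta(3,5). The unit probability mass is the posterior probability of an interval divided by its length. With the stated interval (0.25, 0.33):

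- under-dosing: 0.2436 / 0.25 = 0.97
- proper dosing: (0.4217 − 0.2436) / 0.08 = 2.23
- over-dosing: 0.5783 / 0.67 = 0.86

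The largest is proper dosing, so Stay. P(p > 0.33) = 0.58, so no flag. On the same assumptions all 27 cells of Table 3 are reproduced. Protocol 9.2.1 also gives a target of 0.33 with margins 0.05 and 0.03, which would make the interval (0.28, 0.36). Under that interval the three masses at 2 of 6 are 1.10, 2.28 and 0.80, still Stay. The entry is what the design produces.

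**2. Does 2 of 6 meet the MTD limit?** 2/6 = 0.3333, which is not below 0.33. Reading 0.33 as a rounded third does not help, because the inequality is strict. The next lower rate observable in 6 patients is 1/6 = 16.7%.

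**3. Is there really no way forward?** Not quite.

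- The dead end uses the trigger in Protocol 3.1.1.2 alone. Under Protocol 3.1 and SAP 2.2 the lower levels arguably do open at 33.3%.
- Those same sections allow the expansion dose to be either the MTD or an RP2D judged tolerable by investigators and sponsor, although Protocol 3.3 names only the MTD.
- Cohorts of 3 or 4 are permitted. A 3 + 4 sequence gives 7 patients, and 2/7 = 28.6% is under the limit, though that sits badly with the cap of 6.

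The passages therefore give conflicting instructions rather than none.

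**4. How likely was the conflict beforehand?** With cohorts of 3 + 3, DL1 continues after 0 or 1 DLT in the first 3. Writing b(k) for the binomial probability of k DLTs in 3 patients,

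P(2 of 6) = b(0)·b(2) + b(1)².

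At p = 0.20: 0.512 × 0.096 + 0.384² = 0.049 + 0.147 = 0.197.

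If instead 4 patients were followed by 2 (an assumption), Table 3 gives Stay at 2 of 4, so no path is cut off and P(2 of 6) = 15p²(1 − p)⁴. The chance of 0 or 1 of 6, (1 − p)⁶ + 6p(1 − p)⁵, is the same for both cohort patterns.

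| Assumed true DLT rate | 2 of 6, cohorts 3 + 3 | 2 of 6, cohorts 4 + 2 | 0 or 1 of 6 |
|---|---|---|---|
| 0.10 | 7.9% | 9.8% | 88.6% |
| 0.20 | 19.7% | 24.6% | 65.5% |
| 0.33 | 26.3% | 32.9% | 35.8% |

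The calculation leaves out the rule that stops a level when its first two patients both have a DLT before the third enrols.

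**5. Can it still affect anything?** SAP Section 6 says DL1 is the only dose level tested, so neither lower-level trigger was acted on. Completion requires a rate below 0.33. With 6 evaluable patients that means 0 or 1 DLT, where the statements agree that DL1 qualifies. SAP 5.1.1 plans no hypothesis test, and SAP 6.1.1.1 only lists and summarizes DLTs.

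**The case for a change.** The case for a change is fair as far as it goes. The conflict lies in current text of both documents, it is no artefact of the table, and at plausible rates it was not remote. A clarification would cost a sentence or two and no patients. The documents give no DLT count for DL1, so a reader cannot confirm from them that 2 of 6 was avoided. Protocol 3.1.2 and SAP 3.1 also let an adverse event be classed as a DLT after consultation, so a later count could differ from the one used when the dose was declared.

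The conflict stands: Table 3's 2-of-6 cell, the cap, the 33% limit and the two triggers would have to be reconciled before these rules were used again. This note takes no view on which should prevail. The rest does not lead to a change. A protocol and SAP are not where an observed count belongs; the study report is, and the planned DLT listing and summary supply it. No reclassification is reported, so that remark is conjecture. The apparent contradiction at 2 of 3 depends on giving one fixed meaning to an undefined phrase. Protocol 3.1.1.2 itself separates de-escalation with a possible return (2 of 3) from a level considered intolerable (3 of 3), so the overview wording may be shorthand for a de-escalation call.

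**Conclusion.** The inconsistency is genuine, but correcting it now brings no gain. Before the trial, the chance of DL1 ending at 2 of 6 was roughly 8% to 26% with cohorts of 3 + 3, or 10% to 33% with 4 + 2, over assumed true DLT rates of 0.10 to 0.33. Now the remaining effect on the trial's conduct and analyses is nil: the stage governed by these rules is over, no lower level was opened, and the outstanding DLT output is descriptive. This rests on SAP Section 6 being an accurate record and on the completion rule having been followed. The documents support the first directly. The second cannot be checked without the DL1 count, which the study report can give together with the rule applied. Rewriting the rules would not alter either.

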3.3. Dose Expansion Phase Test Dose Definition

The Expansion Phase Test Dose will be the MTD identified in the Dose Finding Phase. Further experience in the Dose Expansion Phase cohort may result in the need to explore a lower Dose Expansion Phase Test Dose.

3.3.1. Dose Expansion Phase

The Dose Expansion Phase Test Dose identified in the Dose Finding Phase will be expanded up to an additional 40 patients with the purpose of confirming the safety, efficacy, PK, and PD of that dose.

In case both DL-1A and DL-1B regimens are identified as Dose Expansion Phase Test Doses, both of them will be expanded up to an additional 40 patients randomly enrolled in each arm.

3.4. Recommended Phase 2 Dose Definition

The RP2D is the dose of avelumab and axitinib in combination chosen for further studies based on Phase 1 study results. If the MTD proves to be clinically feasible for long-term administration in a reasonable number of patients, then this dose usually becomes the RP2D. Further experience with the MTD may result in a RP2D dose lower than the MTD. Attention will be given to the percentage of patients that discontinue treatment due to treatment-related AEs, especially (both early and late occurring) immune-related (dose-limiting) toxicities.

4. PATIENT SELECTION

This study can fulfill its objectives only if appropriate patients are enrolled. The following eligibility criteria are designed to select patients for whom participation in the study is considered appropriate. All relevant medical and non-medical conditions should be taken into consideration when deciding whether a particular patient is suitable for this protocol.

4.1. Inclusion Criteria

Patient eligibility should be reviewed and documented by an appropriate member of the investigator's study team before patients are included in the study.

Patients must meet all of the following inclusion criteria to be eligible for enrollment into the study:

1. Diagnosis:
 - Histologically or cytologically confirmed advanced RCC with clear cell component;

- Primary tumor resected;
 - A formalin-fixed, paraffin-embedded (FFPE) tumor tissue block from a *de novo* tumor biopsy obtained during screening will be required (biopsied tumor lesion should not be a RECIST target lesion). Alternatively, a recently obtained archival FFPE tumor tissue block (not cut slides) from a primary or metastatic tumor resection or biopsy can be provided if the following criteria are met: 1) the biopsy or resection was performed within 1 year of enrollment AND 2) the patient has not received any intervening systemic anti-cancer treatment from the time the tissue was obtained and enrollment. If an FFPE tissue block cannot be provided as per documented regulations 15 unstained slides (10 minimum) will be acceptable (see [Section 6.1.1](#)).
 - Availability of an archival FFPE tumor tissue block from primary diagnosis specimen (if available and not provided per above). If an FFPE tissue block cannot be provided, as per documented regulations, 15 unstained slides (10 minimum) will be acceptable (see [Section 6.1.1](#));
 - At least one measurable lesion as defined by RECIST version 1.1 that has not been previously irradiated.
2. Evidence of a personally signed and dated informed consent document indicating that the patient (or a legally acceptable representative, as allowed by local guidance/practice) has been informed of all pertinent aspects of the study.
 3. Patients who are willing and able to comply with scheduled visits, treatment plans, laboratory tests, and other study procedures.
 4. Age ≥ 18 years. (≥ 20 years in Japan).
 5. Estimated life expectancy of at least 3 months.
 6. Eastern Cooperative Oncology Group (ECOG) performance status (PS) 0 or 1 (see [Appendix 1](#)).
 7. No evidence of pre-existing uncontrolled hypertension as documented by 2 baseline blood pressure (BP) readings taken at least 1 hour apart. The baseline systolic BP readings must be ≤ 140 mm Hg, and the baseline diastolic BP readings must be ≤ 90 mm Hg. Use of antihypertensive medications to control BP is allowed.
 8. Adequate bone marrow function, including:
 - a. Absolute neutrophil count (ANC) $\geq 1,500/\text{mm}^3$ or $\geq 1.5 \times 10^9/\text{L}$;
 - b. Platelets $\geq 100,000/\text{mm}^3$ or $\geq 100 \times 10^9/\text{L}$;
 - c. Hemoglobin ≥ 9 g/dL (may have been transfused).

9. Adequate renal function, including:
 - a. Estimated creatinine clearance ≥ 30 mL/min as calculated using the Cockcroft-Gault (CG) equation;
 - b. Urinary protein $< 2+$ by urine dipstick. If dipstick is $\geq 2+$, then 24-hour urinary protein < 2 g per 24 hours.
10. Adequate liver function, including:
 - a. Total serum bilirubin ≤ 1.5 x upper limit of normal (ULN);
 - b. AST and ALT ≤ 2.5 x ULN.
11. Serum pregnancy test (for females of childbearing potential) negative at screening.
12. Male patients able to father children and female patients of childbearing potential and at risk for pregnancy must agree to use 2 highly effective methods of contraception throughout the study and for at least 90 days after the last dose of assigned treatment.

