7. Contraception Check: Male patients with female partner of childbearing potential and female patients who are of childbearing potential will need to affirm that they meet the criteria for correct use of 1 of the selected methods of contraception. The investigator or his or her designee will discuss with the patient the need to use 1 highly effective contraception method consistently and correctly and document such conversation in the patient's chart. In addition, the investigator or his or her designee will instruct the patient to call immediately if the selected contraception method is discontinued, or if pregnancy is known or suspected in the patient or the patient's partner.

090177e1907c3de0.1\Draft\Versioned On:01-Mar-2019 17:22 (GMT)

8. **Vital Signs:** Vital signs to include: blood pressure, pulse rate. Blood pressure and pulse rate should be taken with the patient in the seated position after the patient has been sitting **quietly** for at least 5 minutes. Two blood pressure and pulse rate readings will be taken at least 1 hour apart at each clinic visit. After amendment #4 approval, required every 6 weeks.
9. **Home Blood Pressure Monitoring:** All patients will receive home blood pressure monitoring devices and blood pressure will be monitored at home. While on axitinib (as a single agent during the Lead-in PK period and in up to 8 patients enrolled for further PK assessment, or when combined with avelumab), patients will monitor their blood pressure at least twice daily (before taking each dose of axitinib), and blood pressure should be recorded in a patient diary. Patients should be instructed to contact the site immediately for guidance if their systolic blood pressure rises above 150 mm Hg, diastolic blood pressure rises above 100 mm Hg, or if they develop symptoms perceived to be related to elevated blood pressure (eg, headache, visual disturbances), although a different blood pressure threshold for contacting the site may be used according to the investigator's clinical judgment (see [Section 5.3.5.2](#)).
10. **Hematology, Blood Chemistry, and Coagulation: Required** tests are listed in [Table 8](#). May also be performed when clinically indicated.

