27. **Anti-Avelumab Antibodies (Anti-Drug Antibodies, ADAs) and Neutralizing Antibodies (Nab):** One blood sample (3.5 mL) for anti-avelumab antibodies will be collected pre-dose on Cycle 1, 2, 3, 4, 6 and 8. Subsequently, testing should be performed approximately every 12 weeks until cycle 50. All samples should be drawn within 2 hours before start of avelumab infusion. Also see the [Schedule for Pharmacokinetic Sample Collection](#) Table. Additional samples for anti-avelumab antibodies (and simultaneous PK draws for measurement of avelumab) will be collected at the Day 30 Follow-up visit after the end of avelumab treatment. All the samples that are positive for ADA may also undergo characterization for Nab. See [Section 7.3](#).
(X) = only if activity not performed in prior 3 days.

**SCHEDULE OF ACTIVITIES for END OF TREATMENT and SHORT-/LONG-TERM FOLLOW-UP Periods
 Patients participating in Dose Finding Phase and up to 8 additional patients enrolled for further PK assessment**

Visit Identifiers ¹	End of Treatment/Withdrawal ²	Post-Treatment Follow-Up	
		Short-Term Follow-Up (Day 30, Day 60, Day 90 [±3 days]) ³	Long-Term Follow-Up (±14 days)
Clinical Assessments			
Physical Examination ⁴	X	X	
Contraception Check ⁵	X	X (only at Fu Day 30)	
ECOG Performance Status	X	X	X
Vital Signs ⁶	X	X	
Laboratory Studies			
Hematology ⁷	X	X	
Blood Chemistry ⁷	X	X	
Coagulation ⁷		If clinically indicated	
Thyroid Function Tests ⁸	X	X	
ACTH ⁹	X	X	
HBV, HCV Tests		If clinically indicated	
Serum/Urine Pregnancy Test ¹⁰	X	X	
Urinalysis ¹¹	X		
12-Lead ECG ¹²	X		
Disease Assessments			
Tumor Assessments (including scans) ¹³		Q6W after Cycle 1 Day 1 up to 1 year after the first dose; Q12W thereafter	
Survival ¹⁴		X	X
Other Clinical Assessments			
Adverse Events ¹⁵		X	
Concomitant Medications/Treatments ¹⁶	X	X	
New Anticancer Therapy	X	X	X

090177e1907c3de0\0.1\Draft\Versioned On:01-Mar-2019 17:22 (GMT)

Visit Identifiers ¹	End of Treatment/Withdrawal ²	Post-Treatment Follow-Up	
		Short-Term Follow-Up (Day 30, Day 60, Day 90 [±3 days]) ³	Long-Term Follow-Up (±14 days)
Other Samplings			
Pharmacokinetics ¹⁷		See SoA for PK	
██████████ CCI ██████████	█	██████████	
De Novo FFPE Tumor Tissue Block ¹⁹	X		
Anti-Avelumab Antibodies and Neutralizing Antibodies ²⁰		See SoA for PK	

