4.3. Life Style Guidelines

4.3.1. Contraception

In this study, patients will receive avelumab (for which the teratogenic risk is currently unknown) in combination with axitinib, which has been associated with teratogenic risk.

The investigator or his or her designee, in consultation with the patient, will confirm that the patient has selected an appropriate method of contraception for the individual patient or her partner from the permitted list of contraception methods (see [Section 4.3.1.4](#)) and will confirm that the patient has been instructed in its consistent and correct use. At time points indicated in the [Schedule of Activities \(SoA\)](#), the investigator or designee will inform the patient of the need to use highly effective contraception consistently and correctly and document the conversation and the participant's affirmation in the patient's chart (participants need to affirm their consistent and correct use of at least 1 of the selected methods of contraception).

Patients must agree to use at least 1 of the selected methods of contraception throughout the study and continue to do so for at least 30 days after the last dose of study treatment. In addition, the investigator or designee will instruct the patient to call immediately if the selected contraception method is discontinued or if pregnancy is known or suspected in the participant or partner.

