4.3.1.1. Male Participant Contraception

Male patients with female partner of childbearing potential must agree to use a male condom during the intervention period and for at least 30 days after the last dose of study treatment.

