4.3.1.2. Female Participant Reproductive Status

A female patient is eligible to participate if she is not pregnant or breastfeeding and at least 1 of the following conditions applies:

- Is not a Women of Childbearing Potential (WOCBP) (see definitions in [Section 4.3.1.3](#)).

OR

- Is a WOCBP and using a contraceptive method that is highly effective (with a failure rate of <1% per year), preferably with low user dependency, as described below during the intervention period and for at least 30 days after the last dose of study treatment. The investigator should evaluate the effectiveness of the contraceptive method in relationship to the first dose of study intervention.

The investigator is responsible for review of medical history, menstrual history, and recent sexual activity to decrease the risk for inclusion of a woman with an early undetected pregnancy.

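### Inclusion criterion 12 asks for 2 highly effective contraceptive methods for 90 days after the last dose; Sections 4.3.1 to 4.3.1.2 ask for 1 method, or a condom, for 30 days

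*Protocol*

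**What the plan says.** Protocol Section 4.1, criterion 12, covers men able to father children and women of childbearing potential at risk of pregnancy. They "must agree to use 2 highly effective methods of contraception throughout the study and for at least 90 days", counted from the final dose. The same section makes every inclusion criterion a condition of enrolment.

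Section 4.3.1 asks that each patient "use at least 1 of the selected methods of contraception throughout the study and continue to do so for at least 30 days", again counted from the final dose, with methods drawn from the permitted list in Section 4.3.1.4. Under Section 4.3.1.1, men whose female partner could become pregnant "must agree to use a male condom during the intervention period and for at least 30 days after the last dose of study treatment". Section 4.3.1.2 is worded as an eligibility rule: "A female patient is eligible to participate if she is not pregnant or breastfeeding and at least 1 of the following conditions applies". One of its conditions is that a woman of childbearing potential uses a highly effective method, "as described below during the intervention period and for at least 30 days after the last dose of study treatment".

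The contraception footnotes to the Schedules of Activities (footnotes 7 and 5 for Dose Finding, 6 and 5 for Dose Expansion) have the investigator discuss "the need to use 1 highly effective contraception method consistently and correctly" and give no post-treatment duration. In both follow-up schedules the check is made at End of Treatment and then at follow-up Day 30 only.

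**The concern.** Two operative rules give different minimums for the same patients, and one of the shorter ones is itself phrased as an eligibility condition. Both are current, unredacted text. Section 4.3.1 says that axitinib has been associated with teratogenic risk and that avelumab's risk is unknown, so the length of post-treatment contraception matters for safety. A site working from Sections 4.3.1 to 4.3.1.2 and the schedule would let contraception stop at Day 30, although the patient's agreement at entry ran to Day 90. A site could also accept a patient under Section 4.3.1.2 whom criterion 12 excludes.

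**Working it through.** The plan gives no calculated figure here, so the check is a comparison of texts.

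| Protocol place | Applies to | Methods | After last dose |
|---|---|---|---|
| 4.1, criterion 12 | Men able to father children; at-risk women of childbearing potential | 2 highly effective | at least 90 days |
| 4.3.1 | Patients generally | at least 1 from the list | at least 30 days |
| 4.3.1.1 | Men with a partner of childbearing potential | male condom | at least 30 days |
| 4.3.1.2 | Women of childbearing potential | 1 highly effective | at least 30 days |
| Schedule footnotes | Both sexes | 1 highly effective | not stated |

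**Gap between the minimums.** Methods: 2 − 1 = 1. Duration: 90 − 30 = 60 days.

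**Women.** Sections 4.3.1 and 4.3.1.2 set floors.
- Two methods for 90 days satisfies criterion 12 and both later sections.
- One method for 30 days satisfies Sections 4.3.1 and 4.3.1.2 and fails criterion 12.

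The mismatch runs one way only.

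**Men.** Section 4.3.1.4 lists the highly effective methods, and the male condom is not among them. Taking a man with a partner of childbearing potential, and letting methods used by the partner count:
- Two listed methods and no condom, for 90 days: meets criterion 12, fails Section 4.3.1.1.
- Condom alone: meets Section 4.3.1.1 and fails criterion 12. It arguably fails Section 4.3.1 too, since that section draws on the same list.

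The mismatch runs both ways, so following criterion 12 alone does not guarantee compliance with Section 4.3.1.1.

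**Follow-up checks.** Short-term follow-up visits fall at Days 30, 60 and 90. The contraception check is made at 1 of the 3. Women of childbearing potential are pregnancy-tested at all 3 and at End of Treatment (footnote 10 of both follow-up schedules; Section 7.1.1 requires testing at end of treatment and through short-term follow-up).

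**The case against.** The strongest reply is that the rules can be read together. Section 4.1 requires every inclusion criterion to be met, and the later sections say at least 1 method and at least 30 days, so the stricter rule simply binds. For enrolling women this stands. A reader might infer that sites are free to choose between two enrolment standards; the documents do not support that, because Section 4.3.1.2 cannot waive a mandatory criterion. The reply does not cover men, for whom neither rule contains the other. Nor does it cover post-treatment counselling, where the sections that sites work from state 30 days.

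A reader might also infer that the condom could serve as one of criterion 12's two methods. Section 4.3.1.4 points the other way, since criterion 12 asks for highly effective methods and that list omits the condom.

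A second reply is that safeguards already exist, and this largely stands. Besides the pregnancy tests, patients are told to "call immediately if the selected contraception method is discontinued or if pregnancy is known or suspected in the participant or partner". Section 8.10 requires a report within 24 hours of awareness when a patient or partner is found to be pregnant during the patient's treatment, with follow-up to outcome. So a reader should not conclude that partner pregnancies go unrecorded. These measures detect or report pregnancy, however. They do not prevent it, and none is a scheduled check of contraceptive use after Day 30.

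A third reply is that a Day 30 check is a shortfall only if 90 days is the intended rule. That is correct, and the documents do not settle which duration is medically right. Closed enrolment would not remove the question, because the duration applies after each patient's last dose.

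**Conclusion.** The inconsistency holds as a minor consistency and safety correction. Its size is a difference between stated rules of 1 method and 60 days. It should not be read as a demonstrated 60-day loss of protection: the documents show what sites are told, not what patients did. They also do not give the number of patients of reproductive potential, so the number affected cannot be estimated. The DLT endpoint, the sample size and all planned analyses are untouched.

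Two assumptions apply. Saying that patients agreed to 90 days assumes that criterion 12 read as it does now when they enrolled; earlier protocol versions are not available to check. The two-way mismatch for men assumes that a partner's methods count toward criterion 12.

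**What to change.** State one number of methods and one post-treatment duration, identical in criterion 12, Sections 4.3.1 to 4.3.1.2 and the schedule footnotes. State that the male condom is additional to the highly effective methods in Section 4.3.1.4, or amend that list. The sponsor should choose the rule from the drugs' safety information. If it documents that 30 days is enough, correcting criterion 12 to match settles the duration. Otherwise, put 90 days into Sections 4.3.1 to 4.3.1.2 and extend the contraception check to the Day 60 and Day 90 visits. The cost is amendment wording and, under the 90-day option, one added question at visits already scheduled.
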